#### 7.6.5.2 Confrontational Visual Fields

The Blinded Evaluating Investigator will:

- Sit face to face with the subject
- Have the subject cover their left eye with hand or occlude
- The investigator covers their right eye
- Instruct the subject to continuously stare at the investigator's nose
- The investigator stares continuously at the subject's nose
- The investigator extends their left arm with finger pointed inward from far left side and gradually moves their finger toward the midline
- Ask the subject to indicate when they see the finger
- Repeat test for top of visual field (arm and finger up high)
- Repeat test for bottom of visual field (arm and finger down low)
- Repeat all three tests for the other eye

Normal finding: Subject reports seeing the finger at about the same time or location as the investigator.

Abnormal finding: Subject does not see the finger at about the same time or location as the investigator.

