### 7.6.5.3 Ocular Motility

The Blinded Evaluating Investigator will:

• Have the subject stare at the investigator

- Ask the subject to "follow my finger"
- The investigator will move their finger to extremes of gaze on left, right, top and bottom

Normal finding: Observe eyes to ensure consistent conjugate gaze throughout the test

Abnormal finding: subject does not have consistent conjugate gaze throughout the test

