#### 7.9.3.4 Adverse Events of Special Interest

Certain events will require more detailed and timely reporting. These include:

- any significant changes in vision. A one-line change in the Snellen chart is considered significant and requires reporting as an AESI.
- any events attributable to an embolic or ischemic cause (e.g., skin infarction)
- Any incidence of an event due to an embolic or ischemic cause or visual disturbances (including, but not limited to, any loss of vision, blurry vision, double vision, pain in or around eye, blind spot or shadow in the visual field, trouble moving eyes, etc.) MUST be immediately reported to the Medical Monitor by phone, email or fax. The investigator/coordinator must complete the AE source/CRF page and email or fax it to the Medical monitor as soon as possible after the investigator or coordinator has become aware of its occurrence. These reports will include the depth of injection, the injection volume, the symptoms that were observed, the time to onset, time to resolution, and any

interventions that were implemented. The Sponsor will notify the FDA within 10 working days regardless of relation to investigational device.

In the event of blindness or any ophthalmic signs or symptoms, subjects will undergo immediate evaluation by a retina specialist.

Refer to Appendix 1: Filler First Aid Protocol.

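### The confrontation field test in Section 7.6.5.2 examines only one horizontal side of each eye, so a loss confined to the other side is graded Normal.

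*Combined protocol and SAP*

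**What the plan says.** Section 7.6.5.2 has the blinded Evaluating Investigator face the subject ("Sit face to face with the subject"). For the first eye, the subject's step is "Have the subject cover their left eye with hand or occlude" and the examiner's is "The investigator covers their right eye". Fixation is on the examiner's nose: "Instruct the subject to continuously stare at the investigator's nose". The horizontal presentation is then "The investigator extends their left arm with finger pointed inward from far left side and gradually moves their finger toward the midline". One presentation from above and one from below follow, and the script closes with "Repeat all three tests for the other eye". The result is Normal if the subject sees the presented finger at about the same time or place as the examiner does, and Abnormal otherwise. Appendix 5 repeats that grading and adds no direction.

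Section 7.6.5 schedules the vision evaluations before treatment on Day 1, 30 minutes after treatment, and at Visit 2 (Day 28). Exclusion 5 in Section 7.3.2 makes an abnormal pre-treatment result a bar to entry. Section 7.9.3.4 counts "blind spot or shadow in the visual field" among the visual disturbances that must be reported immediately.

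**The concern.** The script has three presentations per eye, and only one of them is horizontal. The grade depends entirely on the presentations made, so a side that is never presented cannot produce an Abnormal result. Section 7.6.5.3, on ocular motility, names both horizontal sides: "The investigator will move their finger to extremes of gaze on left, right, top and bottom". The field test does not.

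Three uses of the result are affected. A subject with an existing loss on the untested side passes exclusion 5. That subject also carries a Normal baseline, so a loss found later cannot be dated to before or after injection. After treatment, the 30-minute evaluation is the only vision examination scheduled on the day of injection, and Appendix 1 treats retinal ischemia as a matter of minutes (about 90 before damage is permanent). A Normal grade that covers three directions says less than a reader would assume.

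**Working it through.** No statistical calculation applies and the plan states no figure to reproduce. The check is to trace the directions and count them.

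**First eye.**
- The subject's left eye is covered, so the right eye is tested.
- The two people face each other, so the examiner's left is the subject's right.
- A finger entering from the examiner's far left therefore enters from the subject's far right, which is the outer (temporal) side of the right eye.
- It moves toward the midline, and the subject responds on first seeing it. Nothing enters from the nasal side.
- I take the next two steps as covering the upper and lower field, as the section labels them.

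**Second eye.** The closing instruction does not say whether the arm changes.

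| Reading | Right eye, untested side | Left eye, untested side |
|---|---|---|
| Mirrored (right arm, from the examiner's far right) | nasal | nasal |
| Literal (left arm again, from the examiner's far left) | nasal | temporal |

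On either reading, one horizontal side of each eye is never presented.

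**Count.** Against left, right, top and bottom, each eye gets 3 of 4 directions. Over both eyes that is 2 × 3 = 6 of 2 × 4 = 8, so 2 of 8 are untested, and this recurs at each of the 3 scheduled evaluations. The figures count steps and do not estimate missed events.

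**Does anything else in the protocol supply the missing side?**
- Appendix 5 has the same grading and no added direction.
- The visit lists in Sections 7.7.1, 7.7.3 and 7.7.6 name the test without describing it.
- Ocular motility (Section 7.6.5.3) covers left and right, but grades whether the eyes move together. It does not test the field.
- Snellen acuity (Section 7.6.5.1) is done for each eye and grades any change from the PRO 2018-02 baseline as abnormal. It can catch a loss affecting acuity, but not one that spares it.
- The calls on Days 3, 14, 56 and 168 (Sections 7.7.2, 7.7.4 and 7.7.5) ask directly about vision changes. They can catch a loss the subject has noticed.

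What remains is a loss confined to the untested side, clear of the top and bottom paths, sparing acuity, and not noticed or not reported by the subject.

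**The case against.** The strongest reply is that this is one of three vision checks at each evaluation and that the plan has other routes to detection. That largely stands. A reader might infer that any nasal loss in either eye would be graded Normal. The documents do not support that: a loss reaching the upper or lower path can be picked up by those two steps, and one affecting acuity can show on Snellen. Nor do they support saying that nasal is the missed side in both eyes as a matter of text. That follows from the mirrored reading, which is the natural one but is not written down.

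A reader might also infer that detection then rests on the subject volunteering a symptom. That is wrong for the four telephone calls, where the question must be asked. The diary, unscheduled visits and immediate reporting of visual disturbances are further routes. None of them helps with a loss the subject has not noticed.

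Two further objections carry some weight. The protocol sets no four-direction standard for this test, so the count uses an outside yardstick, with the motility section as the only comparison inside the document. The evaluators are also described as trained, and some may add the fourth direction by habit. The training material is not available here. Even so, the protocol does not require that step, so sites may differ, and a Normal grade would not show which directions were examined.

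**Conclusion.** The gap is real but narrow. Followed exactly, Section 7.6.5.2 leaves one horizontal side of each eye's field unexamined at all three scheduled evaluations, and a loss confined to that side satisfies the written definition of Normal. This rests on the face-to-face geometry in the section itself, and the finding of one untested side per eye holds whichever way the second-eye instruction is read.

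The effect is on the sensitivity of a safety and eligibility screen. No efficacy endpoint, analysis population or sample-size figure is touched. The documents give no frequency for losses of this kind, so no event count can be attached. Severity: minor, worth correcting because the correction is so cheap.

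**What to change.** In Section 7.6.5.2:
- add a sweep from the opposite horizontal side of the tested eye;
- state which arm and which side apply to each eye;
- change the count in the closing instruction from three tests to four.

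If site training already covers the fourth direction, the protocol text needs only to say so. Recording the result by eye and direction would make a Normal grade easier to interpret, but that is optional, and the current case report form is not in the documents.

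The cost is one or two protocol lines and a few seconds per eye, with the same examiner at the same visits. As a protocol revision it needs the sponsor and IRB approval described in Section 10.5, so it could travel with any other amendment.

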### 7.6.5.3 Ocular Motility

The Blinded Evaluating Investigator will:

• Have the subject stare at the investigator

- Ask the subject to "follow my finger"
- The investigator will move their finger to extremes of gaze on left, right, top and bottom

Normal finding: Observe eyes to ensure consistent conjugate gaze throughout the test

Abnormal finding: subject does not have consistent conjugate gaze throughout the test

### 7.6.6 Prior and Concomitant Medication/Treatment Review

Concomitant medications (including prescription, OTC, and dietary supplements taken and other treatments and cosmetic products used by the subject) will be reviewed with the subject at each study visit and telephone contact. For subjects who did not participate in PRO 2018-03, prior medications/treatments, including the necessary washout times will be reviewed with the subject. A record of prior medications/treatments taken or used by the subject within 6 months before signing the ICF will be obtained at Visit 1/Day 1.

## 7.6.7 Review Inclusion/Exclusion Criteria

The inclusion and exclusion criteria will be reviewed by the investigator or qualified designee to ensure that the subject qualifies for the study.

## 7.6.8 Urine Pregnancy Test and Acceptable Contraceptive Methods

Women of childbearing potential, in addition to having a negative urine pregnancy test at Visit 1/Day 1, must be willing to use an acceptable form of birth control during the study. The following are considered acceptable methods of birth control for the purpose of this study: oral contraceptives, contraceptive patches, contraceptive implant, vaginal contraceptive, double barrier methods (e.g., condom and spermicide), contraceptive injection (Depo-Provera®), IUD, hormonal IUD (Mirena®), and abstinence with a documented second acceptable method of birth control if the subject becomes sexually active. Subjects entering the study who are on hormonal contraceptives must have been on the method for at least 90 days prior to the study and continue the method for the duration of the study. Subjects who had used hormonal contraception and stopped must have stopped no less than 90 days prior to Visit 1/Day 1.

## 7.6.9 Reason for Study Participation Question

Subjects will be provided with the Study Participation Question which asks, "Why did you choose to enroll in this study?" with the following choices:

- Was happy with results and wanted a little more product
- Fullness has diminished and lips are back to original condition
- Other

## 7.6.10 Lip Fullness Grading Scale

The LFGS is a validated 5-point photonumeric rating scale that was developed to objectively quantify the 3-dimensional fullness of the lip. The scale ratings are 0 for very thin, 1 for thin, 2 for moderately thick, 3 for thick, and 4 for full (Carruthers et al, 2008). Photographs illustrating the ratings will be provided to each site. The assessments of overall lip fullness considering both

lips together, fullness of the upper lip, and fullness of the lower lip will be performed at each study visit by the Blinded Evaluating Investigator.

## 7.6.11 Perioral Lines at Rest Severity Scale

The POL is a 4-point rating scale that corresponds to the most severe perioral line attribute when the subject's mouth is at rest with the following ratings (Cohen et al, 2014):

- 0. None a mouth with no perioral lines
- 1. Mild a mouth with a few shallow perioral lines
- 2. Moderate a mouth with some moderate lines
- 3. Severe a mouth with many deep lines or crevices

The assessments of overall perioral lines at rest severity considering both lips together, perioral lines at rest severity of the upper lip, and perioral lines at rest severity of the lower lip will be performed at each study visit by the Blinded Evaluating Investigator.

## 7.6.12 Lip Function Evaluation

Lip function will be assessed by the Blinded Evaluating Investigator by the subject's ability to sip liquid through a straw prior to treatment at each study visit.

## 7.6.13 Lip Sensation Evaluation

Lip sensation will be assessed by the Blinded Evaluating Investigator and tested via: 1) the monofilament test (a subject's ability to feel the sensation of a 0.4G monofilament at 3 points on the upper lip and 3 points on the lower lip), and 2) the cotton wisp test (a subject's ability to feel the sensation of a cotton wisp at 3 points on the upper lip and 3 points on the lower lip) prior to treatment at each study visit.

### 7.6.14 Lip Texture Evaluation

Lip texture will be assessed by the Blinded Evaluating Investigator as normal or abnormal prior to treatment at each study visit (Table 1 Lip Texture Scoring Criteria).

Table 1. Lip Texture Scoring Criteria

Normal	Abnormal			
	Mild	Moderate	Severe	
Texture of the lip is even without visible undulations or excessive coarseness beyond that expected for stated age	The lip shows a single area of textural irregularity (a small papule, area of excess smoothness, focal absence of perpendicular lines) can be visualized only with close inspection	The lip shows more than one area of textural irregularity (a small papule, area of excess smoothness, focal absence of perpendicular lines) can be visualized only with close inspection.  Or  The lip shows one area of textural irregularity (less than ¼ of the lip area) at a conversational distance.	The lip shows two or more areas of textural irregularity (a small papule, area of excess smoothness, focal absence of perpendicular lines) can be visualized at a conversational distance.  Or  The lip shows one area of textural irregularity (more than ¼ of the lip area) at conversational distance	

# 7.6.15 Lip Firmness Evaluation

Lip firmness will be assessed by the Blinded Evaluating Investigator as normal or abnormal prior to treatment at each study visit (Table 2. Lip Firmness Scoring Criteria).

Table 2. Lip Firmness Scoring Criteria

Normal	Abnormal			
	Mild	Moderate	Severe	
Lip is supple when compressed laterally and surface distorted readily with minimal pressure. Pressure with a narrow diameter instrument (cottontipped applicator, toothpick, etc.) causes a focal depression in the surface of the lip. Upon palpation, lip is absent of abnormal structures such as scars or lumps; normal product feel without being visible.	Lip is slightly firm with lateral compression or required slightly greater than normal pressure to distort the surface. Upon palpation, an abnormal structure such as a scar or lump is felt, but is not visible.	Lip is firm with lateral compression or requires distinctly greater than normal pressure to distort the surface or pressure with a narrow diameter instrument (cotton-tipped applicator or toothpick) causes a broader depression in the surface of the lip. Upon palpation, an abnormal structure such as a scar or lump is felt and is visible.	Lip is very firm with lateral compression or requires significantly greater than normal pressure to distort the surface. Upon palpitation, an abnormal structure such as a scar or lump is felt and is visually distracting.	

## 7.6.16 Lip Symmetry Evaluation

Lip symmetry will be assessed by the Blinded Evaluating Investigator as normal or abnormal prior to treatment at each study visit (Table 3. Lip Symmetry Scoring Criteria).

Table 3. Lip Symmetry Scoring Criteria

Normal	Abnormal			
	Mild	Moderate	Severe	
One side of the lip balanced or mirrored the other side	One side of the lip shows a 1 mm or less difference in height or a 1 mm or less difference in the length of the vermilion at repose.	One side of the lip shows a 1.1 mm to 2 mm difference in height or a 1.1 to 2 mm difference in the length of the vermilion at repose	One side of the lip shows a greater than 2 mm difference in the height or a greater than 2 mm difference in the length of the vermilion at repose.	

## 7.6.17 Lip Movement/Function Evaluation

Lip movement/function will be evaluated by the Blinded Evaluating Investigator as normal or abnormal prior to treatment at each study visit as the subject's ability to pucker lips, blowing and pronunciation of words that begin with the letter "W" such as water, work, week and wind.

## 7.6.18 Patient Global Aesthetic Improvement (pGAI) Score

The pGAI score will be recorded at each study visit. Subjects will be asked the question "How would you rate improvement in your appearance compared to your initial condition prior to enrolling in Protocol PRO 2018-02 using the scale below?"

The pGAI score is a 5-point scale with the following categories:

- 1. Worse the appearance is worse than the original condition.
- 2. No change the appearance is the same as the original condition.
- 3. Improved obvious improvement in appearance from the initial condition. A touch-up might further improve the result.
- 4. Much improved marked improvement in appearance from the initial condition, but not completely optimal. A touch-up might slightly improve the result.
- 5. Very much improved optimal cosmetic result.

### 7.6.19 Investigator Global Aesthetic Improvement (iGAI) Score

The iGAI score will be assessed at each study visit by the Blinded Evaluating Investigator.

The iGAI score is a 5-point scale with the following categories:

- 1. Worse the appearance is worse than the original condition.
- 2. No change the appearance is the same as the original condition.
- 3. Improved obvious improvement in appearance from the initial condition. A touch-up might further improve the result.

- 4. Much improved marked improvement in appearance from the initial condition, but not completely optimal. A touch-up might slightly improve the result.
- 5. Very much improved optimal cosmetic result.

## 7.6.20 Swelling Assessment

Swelling will be assessed by the Blinded Evaluating Investigator at each study visit using the 5-point scale with the categories that follow. The Investigator should examine both upper and lower lip simultaneously and recall the degree of augmentation originally provided for comparison. The subject should not be specifically questioned regarding swelling but if the subject spontaneously reports it, such information can be used to assist in selection of a grade for swelling.

- 0. None No swelling noticeable. Lips appear the same as when originally augmented. Any lip enlargement is due to the implanted product only.
- 1. Minimal Slight enlargement of either lip beyond the originally provided augmentation. May or may not be noticeable to the subject but is noticeable to the investigator.
- 2. Mild Some enlargement of either lip beyond the original augmentation that is easily noticeable to the subject, but the lips do not appear abnormally large.
- 3. Moderate Significant enlargement of either lip beyond the original augmentation. Either lip appears abnormally large.
- 4. Severe Any degree of swelling that substantially interferes with lip function such as changes in speech or difficulty eating or drinking.

## 7.6.21 Subject Satisfaction with Lips (Visual Analog Scale [VAS])

Subjects will be asked to assess their overall satisfaction with their lips by using a 100 mm VAS scale from 0 = Very Unsatisfied to 100 = Very Satisfied at Visit 2/Month 1 (Figure 1).

Figure 1 Visual Analog Scale for Subject Satisfaction

## 7.6.22 Investigator Ease of Use Assessment

The Treating Investigator will assess overall ease of use by the device by circling the appropriate number on the numerical rating scale from 0 being not easy to 10 being most easy at Visit 1/Day 1. (Figure 2)

Figure 2 Investigator Ease of Use

0 1 2 3 4 5 6 7 8 9 10 Not Easy Most Easy

## 7.6.23 Subject Pain Score – Visual Analog Scale

Pain from the injection session will be assessed by the subject using a 100-mm VAS scale from 0 = no pain to 100 = worst possible pain at Visit 1/Day 1 immediately after the injection, 15 minutes post the last injection of the session, and at Visit 2. Subjects will be asked the question "How would you rate your pain from the injection of study material?" and will respond by placing a mark on the VAS. (Figure 3)

Figure 3 Visual Analog Scale for Subject Assessment of Pain

## 7.6.24 Treatment Question

At Visit 2 or early termination, subjects and blinded evaluating investigators will be asked to identify which treatment they thought had been administered.

## 7.6.25 Subject Diary Card

A diary card will be dispensed to each enrolled subject at Visit 1/Day 1. The subject will be instructed to complete the diary card to record any AEs experienced during the 2 weeks after receiving treatment. The diary card will be collected at Visit 2/Month 1.

#### 7.6.26 Adverse Events and Serious Adverse Events Assessment

See Section 7.9 for instructions on the assessment and reporting of AEs and SAEs and Section 7.9.7 for instructions on reporting SAEs to the Sponsor or designee.

## 7.7 Visit-Specific Procedures

The following sections outline the procedures required at each visit.

## 7.7.1 Visit 1/Day 1: Treatment

Visit is  $\pm 14$  days of Day 168/Month 6 telephone call for PRO 2018-03 or for subjects enrolled from PRO 2018-02, Visit 1 is Day 1.

- Obtain written informed consent and read and sign the AESI letter dated 04JUN19.
- Update the medical history and demographic information as needed from entry to Protocol PRO 2018-02 and PRO 2018-03
- Perform vital signs (temperature, heart rate, blood pressure, and respiratory rate)
- Vision evaluation (Snellen visual acuity, confrontational visual fields, ocular motility)
- Obtain/record concomitant medications/treatments

- Evaluate inclusion/exclusion criteria
- Perform urine pregnancy test for all women of childbearing potential
- Reason for study participation question
- LFGS assessment
- POL assessment
- Lip function evaluation prior to treatment administration
- Lip sensation evaluation prior to treatment administration
- Lip texture evaluation prior to treatment administration
- Lip firmness evaluation prior to treatment administration
- Lip symmetry evaluation prior to treatment administration
- Lip movement/function prior to treatment administration
- pGAI assessment prior to treatment administration
- iGAI assessment prior to treatment administration
- Swelling assessment prior to treatment administration
- Subject satisfaction with lips (VAS) prior to treatment administration
- Treatment administration waiting 15 minutes after lidocaine cream or inert cream application
- Investigator Ease of Use assessment
- Subject Pain Score immediately after treatment (VAS)
- Subject Pain Score 15 minutes after treatment (VAS)
- Vision evaluation (Snellen visual acuity, confrontational visual fields, ocular motility) 30 minutes post treatment.
- Assess AEs
- Dispense subject diary card
- Schedule next visit
- Complete CRFs

